3. **Sleep interaction:** To characterize the degree to which sleep mediates the effect of suvorexant on drug cue reactivity. We hypothesize an indirect effect of suvorexant on drug cue reactivity via sleep, such that attenuation of cocaine cue reactivity (attentional bias, craving) will be greater in those with larger improvements in sleep duration.

*Conceptual Model:
Orexin System Effects on Relapse Risk*

Figure 1. Summary of Conceptual Model

Research Plan

Our group at the University of Texas Center for Neurobehavioral Research on Addiction (CNRA) has developed, utilized, and validated laboratory models of drug relapse, allowing us to examine pharmacotherapeutic and cognitive-behavioral interventions for relapse prevention.

Study design. To accomplish the project aims, we will utilize a mixed-model experimental design, with a between-groups factor of dose (suvorexant vs. placebo) and a within-subjects factor of time. Subjects will receive suvorexant (**10 mg week 1, 20 mg week 2**) or placebo PO, once daily at 10 PM. Medication condition will be double-blind, with urn-randomized assignment to dose condition balanced by gender and severity of cocaine use. A summary of timelines and measures is shown in the Table below.

Mon	Wed	Fri	Mon	Wed	Fri	Mon
1,4,5,6,7	1,2,3,4,5	1,2,3,4,5	1,2,3,4,5,6,7	1,2,3,4,5	1,2,3,4,5	1,2,3,4,5,6,7
Key: (1) Provide medication (MEMS bottle); (2) Compliance data for medication adherence (MEMS, pill count, riboflavin, text message); (3) Side effects data, med check, UA toxicology; (4) Sleep data; (5) stress /anxiety data; (6) acute stressor challenge (cold pressor); (7) Cue reactivity data						

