Participants and setting. The study will test 30 current cocaine users (enroll 45 to complete 30), 19 to 55 years old, who meet current DSM-5 criteria for cocaine use disorder (CUD) of at least moderate severity (≥ 4 symptoms). Subjects meeting criteria for substance use disorders other than cocaine, marijuana, or nicotine will be excluded. Notably, because the study medication (suvorexant) is contraindicated with alcohol use, we will exclude subjects with alcohol use disorders (via screening at intake). We will also exclude those individuals who are drinking > 10 alcoholic drinks per week (NIAAA criteria problem drinking = at least 14 drinks per week), and who are unwilling to stop using alcohol in the evening for the two weeks of the study. We will exclude those who report binge drinking (NIAAA criteria = in < 2.5 hours, 5 drinks for men, 4 drinks for women).

Other exclusion criteria will include significant and unstable medical/ psychiatric disorders which might make participation hazardous; acute or chronic health conditions; and concomitant medication use contraindicated with the study medication (suvorexant). This will be accomplished via full medical evaluation at intake by [name], M.D., CNRA Medical Director. The study will be conducted at the Neurobehavioral Research Laboratory at the CNRA, directed by [name]. Recruitment strategies will include local advertising in print media, public service announcements on radio, and referrals to CNRA in the Houston metropolitan area. Based on previous and current CNRA recruitment rates of participants with CUD, we expect to enroll 3-4 participants per month to meet recruitment goals.

Measurements

Cue reactivity: Attention bias (AB) task is a saccade-based eye-tracking measurement, developed by [name] to assess attentional bias to drug cues⁴⁸. Eye movements (saccades) have advantages over other variables because they are directly observable, ecologically valid, and typically stable across repeated measures^{49,50}. AB measures utilizing eye movements have produced moderate to robust effects for a broad class abused substances⁵¹⁻⁵³, including cocaine^{34,48,54}. Using our drug specific anti-saccade task, the between-group effect size for anti-saccade error rates in the presence of cocaine cues was large: CUD vs. control Cohen's $d_{av} = 0.6$ ⁴⁸.

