Data Analyses. We will use multilevel modeling to evaluate cue reactivity (attentional bias, craving) as a function of suvorexant, time, and the interaction of suvorexant x time. Hypothesis evaluation will utilize both Frequentist and Bayesian methods. Power and sample size focus on the effect of suvorexant on drug cue reactivity (AB, CCQ). From a Frequentist perspective, assuming a correlation of $r = 0.5$ between measurement points and $\alpha = 0.05$, a sample of $N=30$ participants will provide 80% power to detect a moderate effect (Cohen’s $f = .0.24$) for the interaction if treatment and time. For Bayesian analyses, multilevel priors will be vague and neutral: coefficients ~Normal (mean = 0, variance = 1×10^6), level 1 variance ~ Gamma (shape=.001, scale=.001), level 2 variances ~ Uniform (0,100). Frequentist statistical models will utilize traditional mediation analyses as recommended by Baron and Kenny⁶⁸, which permits unbiased OLS estimates appropriate for this experimental design and sample size⁶⁹, and which we have utilized in previous published research⁷⁰. Bayesian statistical models will utilize path analysis (BSEM) to evaluate the mediating effects of stress/anxiety (biological and subjective-rated) and sleep (biological and subject-rated) for the effects of suvorexant on drug cue reactivity. An example of a mediation analysis using Bayesian SEM may be found Arbuckle⁷¹. Uncertainty surrounding the Bayesian estimate for the indirect effect employs the posterior distribution of the parameter (i.e. the product coefficient): a density denoting the probability that different values of the parameter obtain given the observed data. This approach may be particularly important for evaluating more complex mediation models (e.g. multiple mediators, latent variables) in the context of small sample sizes. Use of the MCMC (Monte Carlo Markov Chain) approach in Bayesian analyses has demonstrated superior small sample performance relative to maximum likelihood-based approaches in continuous, normally distributed data⁷². These properties are likely due to the MCMC approach’s lack of reliance on large sample size assumptions⁷³. BSEM prior specification will adapt recommendations from Muthén and Asparouhov⁷⁴.

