Subject Payment. The payment schedule is detailed below. Subjects will be paid the medication compliance, study visit bonus, and participation earnings at the end of each experimental day (M, W, F). Subjects will receive an additional bonus (\$50) for completing of the study. Total possible payment for meeting all study requirements and collecting all bonus payments will be \$337.

Medication compliance. \$2 for each metric: 1) Medical Event Monitoring System (MEMS) bottle opening, (2) pill counts (empty bag), (3) positive riboflavin markers, and (4) text reply to reminder. Absence of each will result in payment not being earned for that specific metric. Total possible payment = \$8 per day X 14 study days = **\$112**. **Study visit bonus.** \$10 for on time arrival and providing an alcohol-free breath sample and urine sample. Total possible payment = \$10 per day X 7 visit days = **\$70**.

Participation. Total possible payment = \$15 per day X 7 visit days = **\$105**. **Completion bonus \$50**.

Subject participation requirements. Subjects must take the medication as close as possible to 10:00 PM each evening, and reply “yes” to the medication text prompt (texts will be sent at 15-minute intervals from 9:45 PM to 10:30 PM). On M, W, F over 2 consecutive weeks (see Study Design), subjects will visit the lab at 10 AM. At every visit, they will provide the following: medication update (MEMS bottle), side effects data questionnaire, med check up with nurse, UA fluorescence and toxicology, sleep data (wrist monitor and sleep questionnaire), and stress/anxiety questionnaires. The visit will take approximately 1 hour. In addition, on each Monday (day 1, 7, and 14) subjects will complete: (1) the cold pressor test (with cardiovascular measures and saliva sample for cortisol level), (2) the saccade-based attentional bias test, and (3) the cocaine cue reactivity questionnaire. On these three study days, the visit will take approximately 2 hours.

Data Safety Monitoring Plan

E1. Human Subjects Involvement and Participant Characteristics

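### Does calling f = 0.24 a moderate effect overstate what 30 completers can detect?

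*Combined protocol and SAP*

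**What the plan says.** The only sample-size justification is in the Data Analyses section. It states that 30 "participants will provide 80% power to detect a moderate effect (Cohen’s $f = .0.24$) for the interaction if treatment and time", at alpha of 0.05 and "assuming a correlation of $r = 0.5$ between measurement points". The 30 are completers ("enroll 45 to complete 30", Participants and setting).

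The timing comes from two other places. Under Subject participation requirements, "In addition, on each Monday (day 1, 7, and 14) subjects will complete" the cold pressor test, the attentional-bias task and the craving questionnaire, and "subjects will visit the lab at 10 AM". Under Study design, medication is taken "once daily at 10 PM". The first column of the visit table lists no compliance or side-effect items, which agrees with a first session before any dose.

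Nothing in the document turns f into a drug-placebo difference in SDs, questionnaire points or error rate. The one standardised difference given is under Measurements, where "the between-group effect size for anti-saccade error rates in the presence of cocaine cues was large: CUD vs. control", with a value of 0.6.

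**The concern.** For two groups compared once, d = 2f, so f = 0.24 would suggest a difference of about 2 × 0.24 = 0.48 SD. That shortcut fails here. The interaction f is averaged over three sessions, and the first has no expected drug effect, so a given f needs a larger difference at the later sessions. A reader who carries the word moderate over to the drug-placebo difference would think the design about twice as sensitive as it is. The Measurements section sharpens the contrast by calling 0.6 large.

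What would be at stake is the reading of a null result: the sentence could be cited as showing that a moderate drug effect had been ruled out, when differences of half an SD or more remained possible.

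**Working it through.** **Inputs.** Two groups (Study design); m = 3 cue-reactivity sessions (Subject participation requirements); N = 30, r = 0.5, alpha = 0.05, f = 0.24 (Data Analyses). The f is printed with a stray leading point. Assumed: 15 per arm (urn randomisation, no ratio stated), equal SDs at each session, compound symmetry.

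**1. The plan's own figure.** For the group-by-time interaction in a repeated-measures ANOVA:

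- λ = f² × N × m / (1 − r) = 0.0576 × 30 × 3 / 0.5 = 10.368
- df = (2 − 1)(3 − 1) = 2 and (30 − 2)(3 − 1) = 56
- power = 0.808

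Two sessions would give 0.718 and seven 0.970, so three is the basis. An f of 0.20 gives 0.643 and 0.25 gives 0.841, so 0.24 is the intended value and the stray point is a clerical slip. Without the 1/(1 − r) factor, λ = 5.184 and power is 0.496, so the plan's f is in units of the single-session SD.

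**2. Conversion to a difference.** Let d_j be the drug-placebo difference at session j in single-session SDs, with d₁ = 0 because day 1 is before dosing. Then f = ½ √[mean of (d_j − d̄)²].

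- Step (0, d, d) or late onset (0, 0, d): mean squared deviation = (4/9 + 1/9 + 1/9)d²/3 = 0.2222d²; f = 0.2357d; d = 0.24/0.2357 = 1.02.
- Linear build-up (0, d/2, d): mean squared deviation = (0.25 + 0 + 0.25)d²/3 = 0.1667d²; f = 0.2041d; d = 0.24/0.2041 = 1.18.

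This conversion does not involve r; only power does. Simulation (20,000 trials per pattern, 15 per arm) gave power of 80.9% for late onset and 80.5% for a step at 1.018 SD, and 80.6% for linear build-up at 1.176 SD.

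**3. What a null result would exclude.** At r = 0.5 the change from day 1 to the last session has SD √[2(1 − 0.5)] = 1. The expected 95% half-width is t(0.975; 28 df) × √(2/15) = 2.048 × 0.365 = 0.748 SD. For the mean of the two later sessions minus day 1, the SD is √0.75 = 0.866 and the half-width is 0.648 SD.

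An estimate of zero for last minus day 1 excludes both 1.02 and 1.18. On the later-mean contrast, a step effect (1.02) and a linear one (0.75 × 1.18 = 0.88) are also excluded. A late-onset effect averages to 1.02/2 = 0.51 there and is not, so that pattern has to be read at the last session.

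**4. Power at 0.6 SD, for scale.** f = 0.2357 × 0.6 = 0.141 (step or late) or 0.2041 × 0.6 = 0.122 (linear). On the 2-df test at r = 0.5, power is 36% and 28%. With a 1-df test matched to the effect pattern, power is 46% for a step (later mean versus day 1) and 37% for linear build-up (linear time). At r = 0.8 the 2-df figures are 75% and 61%.

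**The case for a change.** The strongest case for a change is that this sentence is the sole justification for the sample size, that the implied difference is more than double what the d = 2f shortcut suggests, and that one added clause would prevent the misreading at almost no cost. At 0.6 SD the planned interaction test has only 28–36% power at the plan's own correlation.

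Part of this stands. The conversion is correct, it is absent from the plan, and readers would benefit from it. The rest does not carry:

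- The sentence names its scale (Cohen's f) and its term (the interaction). It makes no claim about a drug-placebo d, and the document has no rule for reading null results from the power statement. The harm depends on a reader moving the label to another scale.
- The 0.6 compares cocaine users with controls. It is not a target drug effect, and the craving questionnaire has no comparable benchmark.
- The 28–36% describes a 2-df test. That matches the power calculation, but Data Analyses specifies multilevel modelling without saying how time is coded. It also holds r at 0.5, while Measurements describes eye movements as "typically stable across repeated measures", so a higher r is plausible for that outcome.

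A related point is that one alpha of 0.05 covers both attentional bias and craving. Testing an outcome at 0.025, as Holm's first step would require, lowers power at f = 0.24 from 0.81 to 0.72. In a small mechanistic study that is a fair trade-off, separate from how f is described.

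**Conclusion.** The concern does not call for a change. The 80% reproduces (80.8%), and moderate is the usual word for an f of this size. The missing piece is a unit conversion that any analyst can supply: about 1.0 SD for step or late onset and 1.2 SD for linear build-up. Writing it down would leave the sample size, visits, test and every stated figure as they are. The feared conflict with a null result is not there on the sentence's own scale, because an estimate of zero with a half-width of 0.75 SD for change to the last session would exclude the 1.02 to 1.18 SD that f = 0.24 implies.

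This rests on 15 per arm, equal SDs, compound symmetry, no difference on day 1 and, for the half-widths, r = 0.5. If sphericity failed with ε = 0.75, power would be about 72%. Smaller differences, around 0.6 SD, would often be missed, but the plan does not claim otherwise.

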Novelty and promise of the orexin system. The orexins are a class of recently discovered amino acid peptides concentrated in the hypothalamus with projections widely distributed throughout the brain. Two orexin receptors (OXR1, OXR2) have been identified. The orexin system is neuromodulatory, increasing neural action potentials via the regulation of glutamate and GABA. Its primary role appears to be in *energy homeostasis* (e.g., arousal, vigilance). Accordingly, antagonism (blockade) of OXR1 and OXR2 promotes sleep^{39,40}. In addition, there is strong preclinical and phase 1 evidence that orexin antagonists modulate three key cocaine-related variables documented above: sleep^{39,40}, stress/anxiety⁴¹⁻⁴³, reactivity to stimulant drug cues, including cocaine⁴⁴⁻⁴⁷. Only one approved FDA compound with specificity for the orexin receptor system (**suvorexant**) is currently available in the US market. It is indicated for treatment of insomnia. We propose that, due to the ability to regulate stimulant drug-cue reactivity, anxiety/stress, and sleep, suvorexant is an intriguing and potentially efficacious compound for the prevention of relapse in CUD.

Summary. Medications that attenuate drug cue reactivity (attentional bias, craving), reduce stress/anxiety, and enhance sleep quality may be effective pharmacotherapeutics for SUD. As these three factors all contribute to relapse, orexin receptor antagonists may be ideally suited to address the dynamic interaction of these factors, thereby helping in the prevention of relapse.

[figure not shown]
Overall Aim. According to the conceptual model posited in Figure 1, the overarching aim of this project is to conduct a first-in-human drug user study to examine the effects of the orexin antagonist suvorexant on drug-cue reactivity and its interactions with stress/anxiety and sleep.

HYPOTHESES and SPECIFIC AIMS

1. **Main effect:** To characterize the direct effect of suvorexant on drug cue reactivity. We hypothesize that suvorexant will significantly attenuate cocaine cue reactivity (attentional bias, craving).
2. **Stress/anxiety interaction:** To characterize the degree to which stress/anxiety mediates the effect of suvorexant on drug cue reactivity. We hypothesize an indirect effect of suvorexant on drug cue reactivity via stress/anxiety, such that attenuation of cocaine cue reactivity (attentional bias, craving) will be greater in those with larger reductions in stress/anxiety duration.

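### The 80% power is correct for the interaction, but the pre-dose day-1 visit is modelled as an outcome instead of a baseline, which gives up about 3 to 12 points of power

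*Combined protocol and SAP*

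**What the plan says.** Aim 1, under Hypotheses and Specific Aims, reads "Main effect: To characterize the direct effect of suvorexant on drug cue reactivity". Its hypothesis, that cue reactivity will be attenuated, names no day, contrast or model term. Aims 2 and 3 concern indirect effects through stress/anxiety and sleep.

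The Data Analyses section models attentional bias (AB) and craving (CCQ) "as a function of suvorexant, time, and the interaction of suvorexant x time". It does not say how time is coded or whether the first measurement serves as a baseline. It says that power focuses on suvorexant's effect on cue reactivity, and then that N = 30 "participants will provide 80% power to detect a moderate effect" for the interaction, with Cohen's f printed as ".0.24" and read here as 0.24, a correlation of 0.5 and alpha 0.05.

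On timing, the Study design paragraph gives suvorexant "or placebo PO, once daily at 10 PM". Under Subject participation requirements, "subjects will visit the lab at 10 AM", and "on each Monday (day 1, 7, and 14) subjects will complete" the cue-reactivity measures. In the schedule table the first Monday carries no compliance or side-effect code. Day 1 is therefore measured before the first dose.

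**The concern.** Randomisation makes the expected arm difference on day 1 zero. A model with free suvorexant, time and interaction terms ignores this and estimates a day-1 difference that can only be chance. The interaction then measures each later difference against that noisy estimate. Using day 1 as a covariate, or giving both arms one day-1 mean, removes much of this noise with data already collected.

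The heading of Aim 1 adds a second risk. If the suvorexant term averaged over the three visits were taken as the test of Hypothesis 1, it would include a visit at which no drug effect can exist, and the stated 80% would not apply to it. With 30 completers expected from 45 enrolled there is little slack, and a null result on that term could be misread as no drug effect.

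**Working it through.** **Inputs.** From the Data Analyses section: N = 30, r = 0.5, alpha = 0.05, f = 0.24. From the visit schedule: three cue-reactivity visits. Assumed: 15 per arm (the urn randomisation states no ratio), equal variances and correlations, two-sided 1-df tests, complete data.

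**1. The plan's figure.** λ = f²·N·m/(1−r) = 0.0576 × 30 × 3/0.5 = 10.37 with df (2, 56), which gives power **80.8%**. Two visits would give 71.8% and four 87.6%. The 80% therefore belongs to the 2-df interaction over three visits, with day 1 as one of the outcome levels.

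**2. What f = 0.24 means in SD units.** The SD of the three arm differences equals 2f = 0.48. With a day-1 difference of zero:
- step (0, D, D), or one day only, (0, 0, D) or (0, D, 0): SD = 0.4714D, so D = 1.018
- linear (0, D/2, D) or fading (0, D, D/2): SD = 0.4082D, so D = 1.176

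**3. Arm main effect over three visits.** The subject mean has variance (1+2r)/3 = 0.667, so SE = √(0.667 × 2/15) = 0.298 with 28 df. Average effects of 0.679 (step), 0.588 (linear) and 0.339 (day 14 only) give **59%, 48% and 20%**.

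**4. Joint test of days 7 and 14, adjusted for day 1.** Given day 1, each later visit has variance 1−r² = 0.75 and their covariance is r−r² = 0.25. The inverse of this matrix has 1.5 on the diagonal and −0.5 off it. Estimating the slope on day 1 costs a factor 26/27. With day-7 and day-14 differences a and b:

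λ = (15/2) × (26/27) × (1.5a² − ab + 1.5b²), df (2, 54)

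| Pattern | (a, b) in SD | λ | Joint test | Planned interaction |
|---|---|---|---|---|
| Step | 1.018, 1.018 | 14.98 | 93% | 81% |
| Linear | 0.588, 1.176 | 13.73 | 91% | 81% |
| Fading | 1.176, 0.588 | 13.73 | 91% | 81% |
| One day only | 0 and 1.018 | 11.23 | 84% | 81% |

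With an unstructured covariance (26 denominator df) the joint test has about 91%, 89% and 82%. Under the same covariance the planned interaction also loses power: λ = 10.37 with df (2, 27) gives 78%.

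**5. Dependence on r.** Before the 26/27 factor, the ratio of the joint λ to the interaction λ is 3/(1+2r) for step, (2.5+0.5r)/(1+2r) for linear or fading, and 1.5(1+r)/(1+2r) for one day only. At r = 0.5 these are 1.50, 1.375 and 1.125. At r = 0.8 they are 1.154, 1.115 and 1.038. For one day only, 1.038 × 26/27 = 1.00, so nothing is gained.

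**6. Day-14 difference alone, adjusted for day 1.** SE = √(0.75 × (2/15) × (1+1/26)) = 0.322 with 27 df. A difference of 1.018 gives 86% (step or day 14 only) and 1.176 gives 94% (linear). A fading effect leaves 0.588 at day 14, which gives 42%. An effect at day 7 only gives 5%.

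**The case against.** The best defence is that the plan does indicate its test. The power paragraph says that it concerns suvorexant's effect on cue reactivity and then sizes the interaction, which already measures change from the pre-dose visit and is a legitimate test. The heading of Aim 1 is followed at once by a reference to the direct effect and stands against two mediation aims, so it most naturally means unmediated. All of this stands. A reader might infer that Hypothesis 1 has no test at all, or that the study has only 20% to 59% power. The documents do not support either: the interaction is the evident candidate and its 80% is correct. What remains is that no sentence ties it to Hypothesis 1 and that the heading uses the name of a different model term.

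A reader might also note that, with day 1 as reference level, the suvorexant coefficient rejects only about 4% of the time, and call that the low end of the study's power. It is the type I error rate for a difference that is zero by design, and nothing in the plan proposes that coefficient as the test.

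Finally, a day-14 contrast might look like a free improvement. It is a trade-off: 86% to 94% if the effect is at full size on day 14, but 42% if it fades to half and 5% if it is at day 7 only, where the interaction keeps 81%. The increase from 10 mg to 20 mg makes a late peak plausible but does not establish it.

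The objection about r also stands in part. The protocol describes saccade measures as typically stable over repeated testing, so r for AB may exceed 0.5, and the gain there would be smaller.

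**Conclusion.** The concern holds in a limited form. The sample-size figure is correct and needs no change for the interaction. The weakness is that a pre-dose visit is handled as an ordinary outcome visit. At the plan's own r = 0.5, using it as a baseline raises power from 81% to about 93% (step), 91% (linear or fading) or 84% (one day only), so some gain appears in every time course examined. The gain narrows as r rises and is near zero by r = 0.8 for an effect on one day only. These figures rest on 15 completers per arm, equal variances and correlations, and a true effect of f = 0.24, and they apply to each outcome separately at 0.05. The low power of an arm main effect over three visits matters only if that term is taken as the test, which the heading of Aim 1 permits but does not require.

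**What to change.** Add to the Data Analyses section, in substance: Hypothesis 1 is tested, for AB and for CCQ, in the multilevel model with time categorical and both arms given a common day-1 (pre-dose) mean, or equivalently with adjustment for day 1, by the joint 2-df test of the arm differences at days 7 and 14. State the covariance structure and the power of that test with its assumed r, and report the posterior of the same two differences in the Bayesian model.

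If the sponsor expects the effect to be largest at day 14, the day-14 difference adjusted for day 1 may be named instead, with its lower power for fading or day-7-only effects stated.

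Under Hypotheses and Specific Aims, say that "Main effect" in Aim 1 means the direct, unmediated effect and not the arm term averaged over a pre-dose visit. Correct the misprinted f.

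The cost is a few sentences, settled before the data are seen. The joint test spends one slope estimate on the baseline, which is already in the figures above.

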Cue Reactivity: Cocaine Craving Questionnaire (CCQ)⁵⁵ is self-report 14-item measure with five conceptual domains: Desire to Use, Intention to Use, Anticipation of Positive Outcome, Anticipation of Relief from Dysphoria, and Lack of Control over use. The measure is well validated and has been used in multiple studies of CUD^{55,56}.

Sleep: Misfit Shine (Misfit © 2012). Sleep activity is monitored with a 3-axis accelerometer inside the watch device, using a general heuristic based on time and motion. The two primary data outcomes from sleep mode are total sleep and sleep quality (deep sleep duration). The device is waterproof and worn on the wrist 24 hrs per day. Data are downloaded to smartphone via Bluetooth.

Sleep: Pittsburg Sleep Quality Index (PSQI)⁵⁷. The PSQI is an 18-item self-report measure of sleep, providing a well-validated and reliable measure of sleep quality, latency, duration, duration efficiency, and disturbance, and an overall summary. It has been used in several studies of individuals with SUD, including cocaine^{21,58,59}.

Stress/Anxiety: Cold Pressor Test (CPT). The CPT reliably increases activity of the sympathetic nervous system and the HPA axis, and produces reliable increases in heart rate and cortisol^{75,76}. Subjects are requested to submerge the dominant arm up to the wrist or elbow in ice-cold water (0° to 4° C) for as long as possible with a maximum of 90 seconds. The procedure activates afferent nerves and elicits a CNS stress response^{75,76,77}. This procedure produces no lasting biological or psychological distress beyond the acute challenge period, and physiological effects return to baseline within 90 min⁷⁸. In fact, the CPT is used to study pain in children⁷⁹, and is considered a noninvasive, exempt educational experimental activity by the IRB of the University of Texas-Austin⁸⁰. It has been used extensively in cardiology, endocrinology, psychiatry, and psychology since 1940 as a challenge to the peripheral and central stress axis^{75,76}.

Stress/Anxiety: DASS21⁶⁰ is a 21-item self report questionnaire assessing the severity of clinically agreed upon core depression, anxiety, and stress symptoms. It is well validated in multiple languages and countries⁶¹, and has been utilized in SUD treatment and withdrawal studies⁶²⁻⁶⁴.

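### The level-1 variance prior as printed is strongly informative toward zero, and coded literally it can make the Bayesian suvorexant × time intervals far too narrow

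*Combined protocol and SAP*

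**What the plan says.** The Data Analyses section plans a multilevel model of cue reactivity (attentional bias and craving) on suvorexant, time and their interaction. Hypotheses are to be judged by Frequentist and Bayesian methods, and neither is named as primary. On the Bayesian side it states that "multilevel priors will be vague and neutral". The coefficients get a Normal prior with mean 0 and variance 1×10^6. The variances get "level 1 variance ~ Gamma (shape=.001, scale=.001), level 2 variances ~ Uniform (0,100").

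The Gamma is placed on the variance itself and its second parameter is called a scale. The words inverse, precision and rate do not appear, and no prior-sensitivity analysis is planned. The random effects are not listed. The mediation models are covered by a different sentence: "BSEM prior specification will adapt recommendations".

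The Measurements section gives no scoring units or SD for this study's outcomes. For attentional bias it says that "the between-group effect size for anti-saccade error rates in the presence of cocaine cues was large", without saying whether the rate is a proportion or a percentage. The craving scale is a "self-report 14-item measure with five conceptual domains", with no score range.

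**The concern.** The stated intent and the printed distribution contradict each other. The Normal and Uniform priors fit the stated intent; the level-1 prior does not. Its density contains the factor exp(−1000 × variance), which heavily penalises any residual variance much above .001.

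In a random-intercept model the level-1 variance sets the width of the treatment × time interval. An analyst who codes the text as written could report a Bayesian interval that excludes zero when the Frequentist interval on the same data does not, with the prior as the only cause. The conclusion would also change with the units of the outcome, which should not happen under a prior meant to be uninformative.

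**Working it through.** **Inputs from the plan.** N = 30, α = .05 and r = .5 (Data Analyses); f printed with a stray leading point and read as .24 (same section); three cue-reactivity visits (Subject participation requirements: "on each Monday (day 1, 7, and 14) subjects will complete" the cue-reactivity measures).

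**Assumed, because the plan is silent.** 15 per arm; a 95% interval as the Bayesian criterion; complete data; no true effect; a range of outcome SDs. With r = .5 the level-2 variance equals the residual variance σ², so total SD = √(2σ²).

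**1. The plan's own figure.** The plan says that N = 30 "will provide 80% power to detect a moderate effect". For the within-between interaction, λ = N f² m/(1 − r) = 30 × .0576 × 3/.5 = 10.37 on F(2, 56), which gives power of 80.8%. With 2, 4 or 7 measurements it would be 71.8%, 87.6% or 97.0%. So the statement reproduces with three visits and one common correlation ("assuming a correlation of $r = 0.5$ between measurement points"). That is the covariance of a random-intercept model; it supports that model but does not settle it.

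**2. The printed prior.** Mean = .001 × .001 = 10⁻⁶. SD = √.001 × .001 = 3.2×10⁻⁵. P(variance < .001) = .99978. P(variance > .01) = 4.2×10⁻⁹.

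**3. A hand check.** There are 56 within-subject degrees of freedom. With the within-subject sum of squares at its expectation, 56σ², and ignoring the small contribution of the between-subject data, the log posterior for the variance v is −28.999 ln v − 28σ²/v − 1000v. Its mode solves 1000v² + 28.999v − 28σ² = 0.

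- σ² = .5: v = (−28.999 + √(28.999² + 4 × 1000 × 14))/2000 = .105. Width ratio ≈ √(.105/.5) = .46. False exclusion ≈ 2[1 − Φ(1.96 × .458)] = 37%.
- σ² = .005: v = .0042, width ratio .92, false exclusion 7.2%.
- σ² = 50: v = 1.17, width ratio .15, false exclusion 76%.

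**4. Full posterior, random intercept.** Time is categorical, with 56 within-subject and 28 between-subject degrees of freedom and Uniform(0,100) on the level-2 variance. Results are averaged over the chi-square distributions of the sums of squares. Width is relative to the classical interval.

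| Residual variance | Total SD | Printed prior: posterior mean variance | Printed: width | Printed: false exclusion | Inverse-gamma: width | Inverse-gamma: false exclusion |
|---|---|---|---|---|---|---|
| .00125 | .05 | .00124 | .98 | 5.5% | 1.01 | 4.7% |
| .005 | .10 | .0044 | .92 | 6.9% | 1.00 | 4.9% |
| .01 | .14 | .0079 | .88 | 8.4% | 1.00 | 5.0% |
| .04 | .28 | .0224 | .74 | 14.5% | 1.00 | 5.0% |
| .5 | 1 | .105 | .45 | 37% | 1.00 | 5.0% |
| 50 | 10 | 1.16 | .15 | 77% | 1.00 | 5.0% |
| 100 | 14 | 1.65 | .13 | 80% | 1.02 | 4.6% |

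Under the printed prior, false exclusion passes 6% at residual variance .0026 (SD .07) and 10% at .016 (SD .18).

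**5. Same data, two units.** Moving from a proportion to percentage points multiplies the variance by 10,000. An error rate with SD .10 (residual variance .005) becomes SD 10 (residual variance 50), and false exclusion goes from 6.9% to 77%.

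**6. Random intercept and slope, printed prior, true slope variance zero.** Up to residual variance 100, false exclusion is:

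- linear drug × time term: 2.8% to 4.4%;
- middle visit against baseline: about 6% at SD .05, 22% at residual variance .5 and 30% at 100;
- quadratic component: about 7%, 45% and 83% at the same three values.

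The linear protection fails once Uniform(0,100) on the slope variance binds. Coverage of the nominal 95% interval is then .87 to .93 at SD 20 and .57 to .66 at SD 40, with the lower value in each pair for a true slope variance of a quarter of the residual variance.

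**7. A half-correction.** Moving the Gamma to the precision but keeping a true scale of .001 errs the other way: intervals are about 7 times too wide at SD 1 and 1.3 times at SD 10.

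**The case against.** The strongest reply is that this is a one-word slip. The stated intent governs, the other two priors fit it, and adding the word inverse makes the third fit. Entering the same two numbers as shape and rate on the variance is also harmless, with widths within about 1.5% of the inverse-gamma result. Serious harm therefore needs three things together: literal coding, random intercepts only, and outcome units that are not small. The document establishes none of them. The plural in the level-2 prior leaves random slopes open, and the common correlation belongs to the Frequentist power statement, not to the Bayesian model. The plan also states no 95% interval or exclusion-of-zero rule. Finally, a Frequentist analysis of the same hypothesis would make a gross discrepancy visible.

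Most of this stands as a limit on how likely and how large the harm is. A slip is the probable explanation, every SD above is assumed, and for a proportion with small SD the effect is minor. It does not remove the defect. The text is an explicit analysis instruction, it gives wrong intervals if followed, and nothing elsewhere overrides it. Step 7 shows that guessing the repair can fail too. Random slopes protect only the linear term, and not at large units. A discrepancy noticed after the results are known would force a post-hoc choice of prior.

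**Conclusion.** The concern holds. That the printed prior is informative and contradicts the stated intent follows from the text alone, without any assumption. The consequence is conditional. With literal coding and random intercepts, false exclusion of zero ranges from 5.5% (SD .05) through 37% (standardised score) to 80% (residual variance 100), against a nominal 5%. This rests on 15 per arm, complete data, a 95% interval and the assumed SDs. With random slopes the linear interaction is largely protected up to an SD of about 14, but non-linear time contrasts are not.

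The scope is the Bayesian half of Aim 1. The Frequentist analyses, the 80% power statement and the mediation priors for Aims 2 and 3 are untouched. It should be corrected before the Bayesian model is run on unblinded data.

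**What to change.** Replace the level-1 prior with: *level-1 variance distributed as Inverse-Gamma(shape .001, scale .001), equivalently level-1 precision distributed as Gamma(shape .001, rate .001)*. Giving both forms removes the ambiguity over parameterisation, and this line alone cures the error.

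Optionally, put both outcomes on a common scale using one pooled or baseline SD, not standardisation within each visit. This keeps the new prior and Uniform(0,100) from binding at extreme units, where the replacement is otherwise mildly wide (1.31 times the classical width at SD .01, and 1.09 at SD 20).

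The cost is one line of analysis-plan wording and one line of model code, with no extra patients or data collection.
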